# 3.2 Secondary Objectives (or Aim)

The secondary objectives will be to refine efficacy measures for future D-Homes evaluation We will:

- Assess the acceptability of patient-reported outcome measures to detect changes at follow-up visits #1 and #2 (24-30 weeks).
- We will establish and refine laboratory testing protocols for use of a consistent point-of-care A1c machine which our team will control

#### 4 INVESTIGATIONAL PLAN

### 4.1 General Schema of Study Design

This is a randomized pilot trial to inform development of the D-HOMES behavioral treatment, see Tables 1 and 2 above. The intervention, see Figure 2 above, targets diabetes education, motivation and goal-setting support, as well as resource and care coordination for people experiencing type 2 diabetes and homelessness (DH). The goal of this treatment development phase of our work is to refine approaches and protocols for further study of our program.

## 4.1.1 Screening Phase and Baseline Assessment

Recruitment protocols are summarized in section 9.5 below but will involve (1) referral from Health Care for the Homeless, Hennepin Healthcare, supportive housing providers, or other community organizations, (2) snowball sampling using advertisements (flyers, video), word of mouth, and referrals via community partners and previous participants, (3) community advertisement using flyers in places such as bus stops, libraries, and shelters, and (4) invitation letters and follow-up calls to eligible patients at Hennepin Healthcare, (5) invitation letters and follow-up phone calls to eligible Hennepin County clinic patients at Health Care for the Homeless and other willing sites. Per review by the County's internal research review committee (IRRC), these letters and calls will be generated by county employees and handed over to research staff once interested participants are identified, (6) tabling events with study flyers and snacks at Hennepin Healthcare, Health Care for the Homeless facilities, supportive housing or community partners such as libraries, shelters, and drop-in homeless service centers. Potential subjects will be screened in-person or by phone using the protocol inclusion and exclusion criteria.

Congruent with other trials in this area, we will conduct a 2-week run-in period to ensure participants are able to follow-up. During this time two baseline assessment visits will be scheduled. The second baseline assessment visit will be scheduled to correspond to the first treatment visit whenever possible in both the intervention and comparison groups.

### 4.1.2 Study Intervention

This study will be offered to willing participants as an adjunctive to usual diabetes care. No prescriptions will be changed by study staff. Throughout the study, participants will be encouraged and supported to continue seeing their regular health care team. If they do not have one, support will be given to help the participant schedule a primary care or endocrinology appointment at Hennepin County Health Care for the Homeless, Hennepin Healthcare, or another clinic/health system per participant preference.

### 4.1.3 Follow-up

To be eligible for follow-up, subjects must either have completed their planned treatment sessions or requested to end their sessions early. Since the emphasis of this pilot trial is feasibility and acceptability, those ending early will be given particular attention so that their insights and experiences can shape future adaptations to the intervention and study design.

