### 4.3 Study Duration, Enrollment and Number of Sites

### 4.3.1 Duration of Study Participation

Participants will be screened and recruited for a 2-week run-in period. Intervention participants will engage in 10 weekly sessions over 12-weeks with our interventionist ("diabetes wellness coach"), and they will have a 4-week period within which to complete any missed visits. Intervention participants will receive monthly booster calls from coaches after weekly coaching ends through week 24 post enrollment. Comparison participants will engage in a one-time diabetes education session. Comparison participants will receive monthly check-in calls by study staff to update contact information beginning at 6 weeks through week 24. All participants will also complete a two follow-up assessment visits. To maximize participation, these follow-up visits can occur 1 week after intervention and up to 30 weeks after enrollment.

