### 5.2 Study Intervention

For participants randomized to the intervention group, they will be offered 10 coaching sessions over 12 weeks. These will be conducted in-person, via secure video, and/or by phone-based per participant preference and COVID-19 safety protocols. The treatment will center on providing diabetes education, motivational and goal-setting support, and resource and care coordination (Figure 2).

In-person assessment visits will be conducted at private spaces convenient to the participant including Hennepin Healthcare, Health Care for the Homeless sites, or at participant homes (see *Home Visit Protocol*).

All in-person assessment and treatment visits will follow current guidance from HHRI and Hennepin Healthcare about social distancing and use of personal protective equipment.

In-person treatment visits will be arranged that may include the participants home

Video visits will be conducted via a secure Zoom or Teams link (using HHRI, Hennepin Healthcare, and/or Hennepin County HIPAA secure technology) or Facetime if the participant is using an Apple device.

Phone visits will be conducted via a study or office phone or the PI's work phone. If participants have no working phone, a study phone will be issued to participants and will sign a Study Issued Cell Phone/Tablet Agreement (See *Phone/Tablet Agreement*).

Psychological approaches of behavioral activation and motivational interviewing will be used along with provision of educational materials and tools to support behavior change (See *Tools and Education Materials*). Coaches will tailor which tools and educational materials are given to which participants depending on participant need as well as the specific goals that are mutually set. E.g.) A participant with 10 medications per day may benefit from a pillbox with AM and PM slots. E.g.) A participant with many appointments for behavioral and physical health care may benefit from a pocket calendar. Financial value of tools ranges from \$4.99 (glucose log book) to \$17.91 (Adhesives for Continuous Glucose Monitor).

Approved communication channels will be used to support participant's goal setting (e.g. reminders) and arrange study related visits.

Participants will be offered up to 10 treatment visits over 12 weeks and monthly booster calls from weeks 12-24.

#### 5.2.1 Visit 1

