### 5.2.6 Intervention group booster calls

Interventionists will offer monthly booster calls after the end of the intervention period (approx. 12-14 weeks post-enrollment), and prior to the follow-up assessment visit #2. Contact will be limited to a once-monthly to reinforce planned behavioral activation goals, update participant contact information, and arrange final follow up visit.

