### 5.2.7 Comparison Group

Participants randomized into the comparison group will receive one 15 to 30-minute diabetes education session. Interventionists (coaches) will read the content of 3 diabetes educational handouts about (1) general descriptions of type 2 diabetes, (2) healthy eating, and (3) physical activity. Handouts are produced in alignment with American Diabetes Association guidelines by a community group (https://learningaboutdiabetes.org/) and have been used in previous diabetes behavioral trials with participants in low-income situations. Participants will receive a standard pillbox at this visit. Participants will receive a resource sheet with referral information to establish health care, mental health support, or to access local resources for housing, food, and other basic needs.

Comparison group participants will be contacted by the study staff (non-interventionists) once-monthly starting 4 weeks after their education session through the final assessment visit. Booster calls will update participant contact information and remind them of the timeline for follow-up assessments.

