### 5.6 Subject Completion/Withdrawal

Subjects may withdraw from the study at any time without prejudice to their care. They may also be discontinued from the study at the discretion of the Investigator for lack of adherence to study treatment or visit schedules and adverse events (AEs). If the Investigator becomes aware of any serious, related adverse events after the subject completes or withdraws from the study, they will be recorded in the source documents and on the case report form.

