### 5.6.1 Early Termination Study Visit

Any participant who withdraws will be contacted by the PI to be offered the opportunity to complete any outstanding assessment visits with compensation.

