#### 7 STATISTICAL CONSIDERATIONS

# 7.1 Primary Endpoint

The primary endpoint of this study is the satisfaction of participants in this pilot randomized trial (via CSQ-8).

The feasibility and acceptability of study protocols for recruitment, retention, and randomization are also important. We will assess this by measuring our ability to recruit and retain participants, and the assessment and treatment visits we can deliver (i.e., participant's attendance and follow-up with scheduled sessions and treatment activities). In addition to above outcomes, we will carefully track the number and types of between-treatment communications with participants (who initiated communication; form of communication: text, calls, e-mails, etc.).

We will consider the study feasible if we enroll 75% of those screened who meet inclusion criteria, and 75% of enrolled participants complete at least one follow-up. We will consider 50% session attendance as indicative of feasibility. We will consider the intervention acceptable if 70% of participants are satisfied and would recommend it to others.

We will also analyze our primary clinical endpoint of change in A1c between intervention and comparison groups between baseline follow-up visit #1 (approx. 12-16 weeks)

if it changes from baseline to between intervention.

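### Section 4.1.3 makes follow-up depend on finishing sessions or asking to stop, which contradicts the all-participants rule in 4.3.1 and leaves silent non-attenders without a route to outcome assessment

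*Combined protocol and SAP*

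**What the plan says.** Section 4.1.3 sets the condition for entering follow-up: "To be eligible for follow-up, subjects must either have completed their planned treatment sessions or requested to end their sessions early". It then says that those ending early deserve particular attention because the pilot is about feasibility and acceptability.

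Section 4.3.1 carries no such condition: "All participants will also complete a two follow-up assessment visits". Section 7.1 counts retention over enrolled participants, and Section 7.4.1 specifies an intention-to-treat analysis of everyone randomised, with multiple imputation for those lost to follow-up.

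Two further sections deal with people who leave. Section 5.6 lets subjects withdraw and, as a separate route, lets them be "discontinued from the study at the discretion of the Investigator for lack of adherence to study treatment or visit schedules". Section 5.6.1 offers outstanding assessments as follows: "Any participant who withdraws will be contacted by the PI". Neither section defines withdrawal.

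The arms differ in what has to be completed. For D-HOMES, Section 5.2 says: "Participants will be offered up to 10 treatment visits over 12 weeks". For the other arm, Section 5.2.7 says: "Participants randomized into the comparison group will receive one 15 to 30-minute diabetes education session". Table 2 places that single session on the day of baseline visit 2.

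**The concern.** Eligibility for outcome assessment should not depend on what a participant does after randomisation. Section 4.1.3 makes it so. Someone who drifts away from coaching but can still be reached meets neither of its conditions.

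The primary endpoint is the most exposed. Satisfaction by CSQ-8 is collected only at follow-up visit #1 (Table 1), Section 7.4.1 compares it between arms by t-test, and no imputation is stated specifically for it. If silent non-attenders are not assessed, D-HOMES satisfaction is measured among those who finished and those who asked to stop. If the absent are less satisfied, the 70% acceptability criterion becomes easier to meet.

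The loss would probably be informative. The overview in Section 2 reports that in part 2 of the programme engagement fell among those with the greatest housing instability, and housing is the stratification factor in Section 4.2.

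For A1c the intention-to-treat set is not formally reduced, because missing values are to be imputed. The question there is how much outcome data would be imputed that could have been collected. The documents do not allow an effect on the A1c comparison to be estimated.

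**Working it through.** The plan gives no figure to reproduce here, so the check has three parts: coverage of each type of participant, the number of non-completers the plan tolerates, and the consequence for retention.

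**1. Who is covered, on the literal text**

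| Participant | Eligible under 4.1.3 | Offered visits under 5.6.1 | Included under 4.3.1 |
|---|---|---|---|
| Completes planned sessions | Yes | Not needed | Yes |
| Asks to end sessions early | Yes | If this counts as withdrawing | Yes |
| Discontinued by investigator for non-adherence, without having asked to stop | No | Only if discontinuation counts as withdrawing | Yes |
| Stops attending without asking | No | No, unless non-attendance counts as withdrawing | Yes |

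**2. Non-completers implied by the plan's own attendance thresholds**

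Inputs: 54 participants (Section 4.3.2), 1:1 allocation (Section 4.2) and 10 sessions offered (Section 5.2). Section 7.1 says: "We will consider 50% session attendance as indicative of feasibility". The synopsis, under its statistical and analytic plan, puts the threshold at 70%, so both are shown.

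Assumptions: exactly 54/2 = 27 in D-HOMES; planned means all 10 sessions; attendance is sessions attended out of 27 × 10 = 270.

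For a total of S sessions attended, maximum completers = floor(S/10) and minimum non-completers = 27 − floor(S/10).

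- At 50%: S = 0.5 × 270 = 135; floor(13.5) = 13; 27 − 13 = **14** (14/27 = 51.9%).
- At 70%: S = 0.7 × 270 = 189; floor(18.9) = 18; 27 − 18 = **9** (9/27 = 33.3%).

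If everyone attends at least session 1, which Table 2 places on the day of baseline visit 2, c completers need 10c + (27 − c) ≤ S, so c ≤ (S − 27)/9.

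- At 50%: c ≤ 108/9 = 12, giving at least 15 non-completers (15/27 = 55.6%).
- At 70%: c ≤ 162/9 = 18, giving at least 9, as before.

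These are minimum numbers of people who would have to ask to stop in order to qualify. They do not count people barred. The number barred equals non-completers minus those who asked to end early, and the documents do not give the second figure.

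**3. Consequence for the retention criterion (illustration)**

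Section 7.1 requires 75% of enrolled participants to complete at least one follow-up: 0.75 × 54 = 40.5, so 41 people, leaving room for 13 missing. Suppose k D-HOMES participants are barred and everyone else is seen. Follow-up is then capped as follows.

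| k (assumed) | D-HOMES: (27 − k)/27 | Overall: (54 − k)/54 |
|---|---|---|
| 3 | 88.9% | 94.4% |
| 8 | 70.4% | 85.2% |
| 11 | 59.3% | 79.6% |
| 14 | 48.1% | 74.1% |

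Only the last row fails the 75% criterion. In all four rows the arms are followed unequally.

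**The case against.** The strongest reply is that the rest of the plan is inclusive and one sentence is badly worded. Section 4.3.1 has everyone attend two visits within a wide window, Table 1 attaches no attendance condition, Section 5.3 plans assessment reminders, Section 5.6.1 offers outstanding visits with compensation, and Section 4.1.3 itself singles out early-enders for attention. The sentence may have been meant only to mark when follow-up begins. It is fair to infer an inclusive intent. But the sentence sets an eligibility requirement and gives no timing, so staff applying it as written would turn people away.

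Other objections have weight:

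- **Investigator discontinuation.** The heading of 5.6.1 refers to early termination, so withdrawal could be read to include these people. Section 5.6 words the two routes separately, so this is unclear. The firm gap is silent non-attenders.
- **A narrow group.** The rule itself excludes only someone who has stopped sessions, can be reached, and still does not ask to stop. People who cannot be reached are missing under any wording. This is why the number barred could be zero.
- **The percentages.** They rest on pooled attendance and on planned meaning 10 sessions, while Section 5.2 offers up to 10. An individually agreed smaller number would lower the counts.
- **Imputation.** The sentence in 7.4.1 is not expressly limited to A1c and adherence, so its reach to the CSQ-8 is ambiguous. Housing stratum, abstracted A1c and refill history, and claims may explain part of the missingness. None of this justifies leaving obtainable outcomes uncollected.
- **Booster calls.** Section 5.2.6 has coaches "update participant contact information, and arrange final follow up visit" and does not mention follow-up visit #1. Since these calls start at about weeks 12-14, when that visit is falling due, the omission says little, and the conclusion does not depend on it.

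**Conclusion.** The concern holds and should be fixed. Section 4.1.3 contradicts 4.3.1 and sits badly with retention counted over enrolled participants (7.1) and intention-to-treat (7.4.1). Followed as written, it would bar reachable silent non-attenders, mostly in D-HOMES, from the only visit that collects the primary endpoint. The text does not prove that anyone would in fact go unassessed.

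On the stated assumptions, at least 14 of 27 D-HOMES participants at 50% attendance, or 9 of 27 at 70%, would qualify only by asking to stop. The comparison arm, with one session planned for baseline visit 2, would rarely be affected. The number actually barred is unknown, and no bias in A1c is claimed. Confidence is high for the contradiction and for the direction of the imbalance, but the size of any resulting bias cannot be determined.

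**What to change.** Replace the sentence in Section 4.1.3 with:

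> All randomised participants are eligible for and will be invited to both follow-up visits regardless of sessions attended, unless they withdraw consent for assessment.

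State in Sections 5.6 and 5.6.1 that this includes people who stop attending without asking and people discontinued for non-adherence. Report follow-up completion and CSQ-8 completion by arm.

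The cost is protocol wording in three sections, plus invitations within the 54 × 2 = 108 follow-up visits already planned. One small downside is that some D-HOMES participants may be assessed before they finish make-up sessions.

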### 4.2 Allocation to Groups and Blinding

Participants will be randomized to either the intervention or a control group (1:1). Randomization will be stratified by housing type (unstable (e.g., shelter, staying outside) vs.

more stable (e.g., worry about rent payment, supportive or transitional housing)). Randomization will occur after baseline assessment visit #2 via REDCap. Staff who conduct who conduct the follow-up assessment visits will be blind to condition.

### 4.3 Study Duration, Enrollment and Number of Sites

### 4.3.1 Duration of Study Participation

Participants will be screened and recruited for a 2-week run-in period. Intervention participants will engage in 10 weekly sessions over 12-weeks with our interventionist ("diabetes wellness coach"), and they will have a 4-week period within which to complete any missed visits. Intervention participants will receive monthly booster calls from coaches after weekly coaching ends through week 24 post enrollment. Comparison participants will engage in a one-time diabetes education session. Comparison participants will receive monthly check-in calls by study staff to update contact information beginning at 6 weeks through week 24. All participants will also complete a two follow-up assessment visits. To maximize participation, these follow-up visits can occur 1 week after intervention and up to 30 weeks after enrollment.

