Screening	assessment						
Intervention	2. Randomization to:						
	
 
a. Intervention: study intervention with weekly coaching support in person and/or by phone x 12 week
 
						

	b. Comparison: one-time diabetes education session				
Follow-Up	3. Follow-up 1: 12-16-week follow-up assessments and A1c				
	Follow-up 2: 24-30-week follow-up assessments and A1c				
Efficacy Evaluations	• Satisfaction with trial, recruitment, retention rates				
	
 
Hemoglobin A1c measured by point-of-care fingerstick or venipuncture
 
				
	Self-reported medication adherence				
	Self-reported psychological wellness				
	Self-reported diabetes self-management, distress				
	
 
Height, weight, blood pressure
 
				
Safety Evaluations	Subject safety will be monitored by adverse events and rates of early termination of the study. We will also follow safety protocols in case we identify dangerous blood pressure values during assessment visits				
Statistical And Analytic Plan	We hypothesize a satisfactory, feasible, acceptable intervention with adequate recruitment and retention rates. We may see early indicators of improvement in efficacy measures of adherence, glycemic control, and wellness among intervention participants compared to comparison.				
	We will consider the study feasible if we screen 50% of those referred, enroll 75% of those screened who meet inclusion criteria, and 75% of participants complete follow-up. We will consider 70% session attendance as indicative of feasibility. We will consider the intervention				
	acceptable if 70% of participants are satisfied and would recommend it to others.				
	We will use generalized linear models to compare changes in A1c and medication adherence over time in intervention vs. comparison groups according to the ARMS-D measure of diabetes medication adherence while controlling for baseline differences and changes in housing status over time. Adherence will also be examined with pharmacy refill data (continuous medication gap for non-insulin diabetes medications 0-1.0). We will use an intention-to-treat approach including all randomized participants; multiple imputation will generate data for those lost to follow-up. Similar modeling approaches will compare psychological wellness, and other biometric and patient-reported outcomes.				

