Data And Safety Monitoring Plan	[name] (PI) will work closely with study staff to monitor the quality of data collected at assessment. This pilot trial (N=54), does not meet NIH criteria requiring a Data Safety Monitoring Board				

(DSMB), however Drs. [name], [name], and [name] will oversee a detailed safety monitoring plan.

TABLE 1: SCHEDULE OF STUDY ASSESSMENT PROCEDURES

Study Phase	Eligibility screening	Consent, Baseline visit #1	Run-in, Baseline visit #2	Follow-up visit #1	Follow-up visit #2
Visit Number		1	2	3	4
Study Weeks, approximate	0	1	2-3	12-16	24-30
Confirm communication preferences	X	X		X	X
Review Inclusion/Exclusion Criteria	X	X	X		
Informed Consent		X			
Demographics/Medical History/Medication List		X	X		
Medical records and insurance access permissions		X			X
Biometrics: BP, Height, Weight, Hemoglobin A1c (fingerstick/venipuncture)		X	X	X	X
Medication review		X	X	X	X
Self-report survey measures:					
Mental Health Inventory (MHI-5) 			X	X	X
Health-related Quality of Life Short Form (SF-12) 			X	X	X
Problem Areas in Diabetes (5-item PAID) 			X	X	X
Diabetes self-management questionnaire (DSMQ) 			X	X	X
Adherence to Refills and Medications Scales-Diabetes (ARMS-D) 			X	X	X
Self-reported medication adherence (Adherence Starts with Knowledge, ASK-12) 			X	X	X
Basic needs survey 		X		X	X
Lifetime housing status		X			
Current housing status, 30 day recall		X		X	X
Use of substances (ASSIST)		X		X	
Self-reported health care use (NHANES)		X		X	X
Discrimination in Medical Settings Scale 117		X			
Client Satisfaction Questionnaire (CSQ-8) 95				X	

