# TABLE 2: SCHEDULE OF STUDY TREATMENT PROCEDURES

Intervention group,	Comparison group,
10 weekly coaching offered over 12 weeks	
Session #1 in-person on day of baseline assessment visit 2	1 educational session (15-30 min.) offered in-person on
Sessions #2-10 offered in-person or via phone/video	day of baseline assessment visit 2
Monthly booster calls from 12-24 weeks	Monthly calls to retain contact from weeks 3-30

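### Sections 4.1.3 and 4.3.1 conflict with the common 12-16 week follow-up 1 window and permit A1c to be measured later in the coaching arm

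*Combined protocol and SAP*

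**What the plan says.** One set of sections gives a single window with no distinction by arm. The synopsis lists "Follow-up 1: 12-16-week follow-up assessments and A1c". Table 1, in its row "Study Weeks, approximate", puts screening at 0, baseline visit 1 at 1, baseline visit 2 at 2-3, follow-up 1 at 12-16 and follow-up 2 at 24-30. Section 7.1 defines the primary clinical endpoint as the change in A1c "between baseline follow-up visit #1 (approx. 12-16 weeks"), and section 7.2 uses the same timing for the secondary endpoints.

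Another set ties follow-up to the end of treatment. Section 4.1.3: "To be eligible for follow-up, subjects must either have completed their planned treatment sessions or requested to end their sessions early". Section 4.3.1: "To maximize participation, these follow-up visits can occur 1 week after intervention and up to 30 weeks after enrollment". The same section says of coaching participants only that "they will have a 4-week period within which to complete any missed visits".

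Treatment length differs by arm. Coaching is ten sessions over 12 weeks, starting with "Session #1 in-person on day of baseline assessment visit 2" (Table 2). The comparison arm has one education session on that same day. Section 5.2.6 puts the end of the intervention period at "approx. 12-14 weeks post-enrollment", and section 6.1 refers to a 16-week assessment visit.

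The A1c model in section 7.4.1 adjusts for baseline differences and for housing change. It has no term for actual visit time and no rule for values taken outside the window.

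**The concern.** A staff member who follows 4.1.3 and 4.3.1 cannot always follow Table 1. A coaching participant who is still making up sessions is not yet eligible for follow-up under 4.1.3, while a comparison participant satisfies that condition as soon as the single session is over. Any delay this causes can arise in one arm only, and its length depends on something that happens after randomisation, namely how much make-up time is used.

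Missed sessions are foreseeable: section 7.1 accepts 50% session attendance as feasible, and section 2 reports that engagement in part 2 fell among participants with the greatest housing instability. If make-up time is used, the A1c contrast at follow-up 1 mixes the effect of coaching with a difference in elapsed time, and the planned model does not separate them. A late first follow-up also shortens the interval to follow-up 2, which section 7.2 uses to judge whether the A1c change is sustained.

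**Working it through.** **Inputs.** Session 1 falls at study week 2-3 (Tables 1 and 2). Coaching lasts 12 weeks, the make-up period is 4 weeks and the gap before follow-up is 1 week (section 4.3.1). The window is 12-16 weeks (synopsis, Table 1, section 7.1).

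**The plan's own figure.** Counted from session 1 with no gap, 0 + 12 = 12 and 0 + 12 + 4 = 16. These are exactly the window's bounds. They reproduce only on that clock and only without the 1-week gap. Table 1 counts from screening, and 4.3.1 adds the gap.

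**Earliest follow-up 1 in the coaching arm.** Let s be the week of session 1. Without make-up the earliest visit is s + 12 + 1. With full make-up it is s + 12 + 4 + 1. Because the documents do not define enrolment, three clocks were tried. Baseline visit 1 is study week 1, so session 1 comes 1-2 weeks after it.

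| Clock | s | No make-up | Full make-up | Weeks past 16 |
|---|---|---|---|---|
| From session 1 | 0 | 13 | 17 | 1 |
| From baseline visit 1 | 1-2 | 14-15 | 18-19 | 2-3 |
| Table 1 study weeks | 2-3 | 15-16 | 19-20 | 3-4 |

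A 12-week course with no make-up stays inside the window on every clock. Full make-up plus one week passes week 16 on every clock.

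**How much make-up is needed to overrun.** The visit falls after week 16 when make-up exceeds 16 - (s + 13) weeks. That is more than 3 weeks counted from session 1, more than 1-2 weeks from baseline visit 1, and more than 0-1 week on Table 1's clock.

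**Without the 1-week gap.** Full make-up then ends at week 16, 17-18 or 18-19 on the three clocks, an overrun of 0, 1-2 or 2-3 weeks. The conflict disappears only when counting from session 1.

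**Consequences if comparison visits stay at 12-16.** On Table 1's clock, a coaching participant with full make-up is measured at least 19 - 16 = 3 to 20 - 12 = 8 weeks later than a comparison participant. Counted from session 1, the lag is 17 - 16 = 1 to 17 - 12 = 5 weeks. A visit at study week 19-20 leaves 24 - 20 = 4 to 30 - 19 = 11 weeks before follow-up 2.

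**The case against.** The strongest reply is that the plan does set a common window. The synopsis, Table 1 and sections 7.1-7.2 agree on it. The sentence in 4.3.1 is permissive, covers both follow-up visits and gives outer limits to help retention. Table 1 labels its weeks approximate. Section 5.2.6 ends the intervention at 12-14 weeks, and one week later is 13-15, inside the window. The trial is declared under-powered for efficacy, its primary endpoint is satisfaction (CSQ-8), and A1c is measured again at follow-up 2. Assessing after treatment ends is also a legitimate choice in a behavioural pilot.

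Much of this stands, and it rules out three stronger readings that a reader might infer:

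- **That different A1c timing by arm is the planned design.** It is not. The documents conflict, and different timing is something the text permits.
- **That comparison participants could be assessed at study week 3-4, up to about 16 weeks before coaching participants.** This takes one permissive sentence literally against Table 1 and 7.1. Section 5.2.7 starts comparison calls four weeks after the education session, partly to remind participants of the follow-up timeline, so follow-up is expected later.
- **That the least engaged coaching participants are assessed last.** Section 4.1.3 lets those who ask to stop early be assessed sooner, and make-up users are those who come back to finish. The documents give no data on who they will be.

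What the reply does not remove is the condition in 4.1.3, which is mandatory. The 12-14 weeks in 5.2.6 leaves little or no room for the make-up period that 4.3.1 grants.

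**Conclusion.** The point holds as a conflict between sections with a possible effect on one comparison. Following 4.1.3 and 4.3.1 as written, a coaching participant who uses the full make-up period cannot have follow-up 1 until about 1-4 weeks after the common window closes, and the analysis does not account for it. The range reflects the undefined time origin, and the figures assume that all four make-up weeks are used and that the 1-week gap is observed.

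The size of any resulting bias in the A1c contrast cannot be computed. It depends on how many participants use make-up time and on when comparison visits are booked, and the documents give neither. The comparison affected is A1c at follow-up 1, together with the other clinical measures taken at that visit. The recruitment, retention and attendance criteria are not affected. It should still be corrected, because a stated secondary objective is to refine efficacy measures for a later trial, and an endpoint without a fixed time origin serves that objective poorly.

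**What to change.** - Define one time origin, randomisation, for both arms, and use it in the synopsis, Table 1 and sections 4.3.1, 5.2.6, 6.1 and 7.1-7.2. Randomisation takes place at baseline visit 2 (study week 2-3), so 12-16 weeks from it corresponds to study weeks 14-19 on Table 1's present clock (2 + 12 to 3 + 16). The table must be restated accordingly.
- Schedule follow-up 1 within the plan's own 12-16 weeks in both arms, whether or not sessions are complete. For that visit, remove the condition in 4.1.3 and the one-week-after-intervention trigger in 4.3.1.
- Record the actual week of each A1c measurement and report it by arm.
- Add to 7.4.1 a sensitivity analysis that adjusts for actual visit week or excludes out-of-window A1c values. Keep the main analysis on all randomised participants, because visit timing is itself a post-randomisation event.

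**Cost.** The change is to wording and one extra analysis. The make-up period itself need not change. Counted from randomisation, full make-up ends at 12 + 4 = 16 weeks, so only coaching participants still making up sessions when their visit falls due are affected. Those few would have A1c measured before their last make-up session. The same applies to CSQ-8, the primary endpoint, which Table 1 collects only at follow-up 1, and the protocol should say that this is accepted.
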